5.2 Statistical analysis

- 1) Kaplan-Meier statistical analysis was used for survival analysis, log-rank test was used to compare survival curves, and Pearson's chi-square test was used to compare categorical variables. When the p value was less than 0.05, the difference was considered statistically significant.

6. Radiation therapy

Prior to initiating treatment, the primary tumor site should be marked with photographic documentation for subsequent resection. The primary lesion may be identified using tattoos, superficial projections, or metallic markers. These metallic markers can be placed at the tumor center and/or margins. When no intramammary markings are available, external identifiers such as superficial tattoos, mass projections, or diagrams may be employed. Clinical examinations combined with ultrasound imaging should thoroughly evaluate axillary lymph nodes. If ultrasound suggests suspicious axillary lymph nodes during baseline assessment, a guided ultrasound-assisted biopsy should be performed to determine the status of these lymph nodes.

Photography (front, left oblique, right oblique): 1 week before radiotherapy, the day

of radiotherapy end, 1 week before surgery, 1 month after surgery

Radiotherapy: CT positioning is used to delineate the target area and normal tissue for dose assessment.

6.1 Simulation positioning

CT positioning: The patient is placed in a supine position with the affected upper limb abducted to grasp the rod. Positioning fixation is performed using a breast support frame combined with a headplate or a cervical-thoracic integrated frame with cervical-thoracic membrane (TOMO treatment requires prolonged duration and necessitates the use of a cervical-thoracic integrated frame with membrane fixation).

A plain CT scan is performed, with the scanning range extending from below the jawline at the upper boundary to encompass the entire liver at the lower boundary, using 5mm layer thickness and lead wire markers for the entire breast area

The affected shoulder joint (L/R): outlined on the bone window, including the entire humeral head and the joint cavity and articular surface

Affected brachial plexus (L/R): According to the RTOG delineation guidelines, the brachial plexus is delineated from C4-5 to 1cm below the olecranon bone, and the brachial plexus is delineated from the intervertebral foramen to the anterior and middle scalene muscle space, with a uniform diameter of 0.6cm.

Thyroid (thyroid): outline the left and right lobes and isthmus of the thyroid gland.

Esophagus (esophagus): from the entrance of the esophagus to the lower border of the aortic arch.

Liver: The whole liver is required.

The stomach (stomach) is required to be delineated at 2cm below the PTV.

6.3 Radiation therapy plan requirements

Table 3

target section	Limitations	Lymph node drainage area of whole breast/thoracic wall + supraclavicular and internal breast area: 40.05Gy/15 times, 2.67Gy/time/day; lymph node drainage area of axillary area: 37.5Gy/15f,2.5Gy/ times/day; both are 5 times per week and completed in 3 weeks;		
		Dosage indicators	Limitations	
ensemble PTV (PTVsc/PT Vax/PTVim/ PTV)	Prescription dosage	target	D95%	40.05Gy
		Offset is acceptable	V40.05	90%
	Hotspot doses	objective	Dmax	<48Gy
		Offset is acceptable	V48	<1ml
	Hotspot doses	target	V44	<5%
		Offset is acceptable	V48	<1%
Whole body	Hotspot	target	Dmax	<48Gy

organization (Including organized and unorganized sketches)	doses	Offset is acceptable	V48	<1ml
---	-------	-------------------------	-----	------

Normal tissue limit:

normal structure	Limitations	Lymph node drainage area of whole breast/corctaneous wall + supraclavicular and internal mammary region: 40.05Gy/15 times, 2.67Gy/time/day; lymph node drainage area of axillary region: 37.5Gy/15f,2.5Gy/ times/day; both are 5 times per week and completed in 3 weeks;	
		Dosage indicators	Limitations
Heart (left breast cancer)	target	mean dose	<8Gy
	Offset is acceptable		<10Gy
	objective	V5	<45%
	Offset is acceptable		<50%

Heart (right breast cancer)	objective	mean dose	<5Gy
	Offset is acceptable		<6Gy
	target	V5	<30%
	Offset is acceptable		<35%
LAD	objective	V40	<20%
	Offset is acceptable		<25%
RA	objective	V40	<20%
	Offset is acceptable		<25%
Lung on the affected side	objective	mean dose	<15Gy
	Offset is acceptable		<16Gy
	objective	V20	<30%
	Offset is acceptable		<32%
	target	V5	<55%
	Offset is acceptable		<60%
Healthy side of lung	target	V5	<20%
	Offset is acceptable		<25%

Healthy breast	objective	mean dose	<5Gy
	Offset is acceptable		<8Gy
medulla spinalis PRV	target	maximum dose	<30Gy
	Offset is acceptable		<32Gy
Inferior brachial plexus injury	objective	maximum dose	<48Gy
oesophagus	objective	V30	<48Gy
	Offset is acceptable		<50Gy
The shoulder joint on the affected side	target	V30	<30%
	Offset is acceptable		<35%
thyroid gland	objective	mean dose	<28Gy
	Offset is acceptable		<32Gy
Liver (right breast cancer)	objective	V5	<25%
	Offset is acceptable		<30%
Stomach (left breast cancer)	target	V5	<25%
	Offset is acceptable		<30%
Liver (left breast	target	V5	<10%

cancer)	Offset is acceptable		<15%
Stomach (right breast cancer)	objective	V5	<10%
	Offset is acceptable		<15%

6.4 Irradiation dose

- 1) Whole breast \pm Thoracic wall + supraclavicular and internal mammary area lymph node drainage area: 40.05Gy/15 times, 2.67Gy/time/day; axillary area lymph node drainage area: 37.5Gy/15f, 2.5Gy/ times/day;
- 2) If the primary lesion after surgery does not reach pCR, the tumor bed is increased to 13.35Gy/2.67Gy/5F (the total EQD2 of tumor bed = 60Gy);
- 3) If the axilla is non-R0 resection, postoperative residual lesions should be considered for additional treatment. Residual lymph nodes should be routinely divided with 26Gy/13F after surgery, and the total radiation dose before and after surgery should be 66Gy (EQD2)

6.5 Radiotherapy techniques

- 1) All of them adopt whole intensity modulation technology, which can be IMRT or VMAT
- 2) It is recommended that all left breast cancer patients choose respiratory control technology, and right breast cancer patients may consider using respiratory control technology.
- 3) All plans must be physically QA validated before treatment can begin
- 4) Daily CBCT location verification is required during treatment

7. Systemic treatment

The chemotherapy regimen, endocrine therapy, and other pharmacological treatments are standardized according to the latest domestic and international guidelines, along

with recommendations from oncology specialists. The treatment course consists of six cycles: two before radiotherapy and four after radiotherapy. If tumor shrinkage remains below 50% after four cycles of chemotherapy, surgical intervention may be considered. Endocrine therapy and other medications are initiated post-surgery.

8. Surgery

- 1) Breast-conserving surgery is preferred whenever possible; autologous flap transplantation may be considered if the patient strongly requests and accepts the associated risks. The specific procedure is determined by the surgeon
- 2) For patients with trans-quadrant multifocal tumors at diagnosis, radical mastectomy is recommended regardless of the response after neoadjuvant therapy; if it is multifocal in the same quadrant, surgical mode can be selected according to the surgeon's advice;
- 3) If no positive lymph nodes are detected during preoperative axillary assessment, sentinel axillary lymph node biopsy (SLND) may be performed first. For patients with cN1 stage before neoadjuvant therapy, if clinical evaluation after neoadjuvant therapy shows negative axillary lymph nodes and the biopsy retrieves ≥ 3 sentinel lymph nodes with confirmed pathological negativity, axillary lymph node dissection (ALND) may be considered as an option. If metastasis is observed in any sentinel lymph node, ALND should be performed, with specific procedures guided by surgical consultation.

9. Surgical pathology

- 9.1 The size of the primary lesion must be measured
- 9.2 Primary tumors must be graded according to the Nottingham revision of the Bloom & Richardson grading system
- 9.3 The surgical margins must be assessed and reported
- 9.4 Routine immunohistochemical detection of ER, PR, Her2 and Ki67
- 9.5 Pathological response rate (must be classified according to Miller-Payne classification), pCR was defined as: ypT0/Tis ypN0

10. Onboarding process

10.1 The eligible patient shall sign the informed consent form

10.2 Complete radiotherapy as required

10.3 Fill in the CRF form

Any subsequent study-specific procedures or assessments may be performed after the subject signs the informed consent form (ICF)

Screening process schedule:

Research phase	Screening period
flow path	Day 14 to Day 1 (D-14 to D-1)
Sign the informed consent form/assign subject number	X
Demographic data and medical history, smoking history, alcohol consumption history	X
History of previous tumors and previous treatment	X
Inclusion/exclusion criteria	X
Clinical examination and evaluation	
Physical examination, height, weight, blood pressure	X
vital sign	X
Chest, abdomen and pelvis CT (PETCT can be omitted if complete)	X
Breast MRI, brain MRI	X
Whole body bone scan /PETCT	X
Cervical, thyroid and breast ultrasound	selectable
12 lead electrocardiogram	X
echocardiogram	X
ECOG physical score	X
Concomitant medication/treatment	X
Laboratory tests/assessments	
Biopsy of breast mass, axillary lymph node biopsy	X
Pathological results	X

Cancer markers CEA, CA15-3, CA-125	X
routine blood test	X
Blood biochemistry	X
Urinalysis, stool analysis	X
Cardiac markers	X
Thyroid function tests (TSH, free T3, free T4)	X
Coagulation function tests	X
Pregnancy test, serum β hCG	X
HBV, HCV, HIV virus screening	X
Tumor evaluation	
Imaging examination (breast enhanced MRI + whole body enhanced CT is preferred)	X
Tumor lesions were evaluated based on RECIST 1.1	X
Quality of life assessment	X

11. Efficacy evaluation

11.1 Long-term follow-up after surgery (see the follow-up table in Appendix for details).

11.2 The follow-up form should be completed for each follow-up visit, and any tumor recurrence, metastasis and death should be recorded on the follow-up form

11.3 Physical examination, breast and axillary, neck and supraclavicular ultrasound, neck, chest and abdominal CT every 3-6 months for the first two years, bone scan, cranial MR: routine once a year, timely review when relevant symptoms occur.

cCR criteria: Complete absence of enhancement in the primary tumor bed and primary metastatic lymph nodes on MRI after NAC is defined as complete imaging remission. In principle, surgical resection is still recommended for patients who achieve cCR. If resection is not willing for any reason, MDT should be discussed to make a decision.

12. Assessment of acute and late radiotherapy side effects

12.1 Postoperative follow-up for 5 years

12.2 The follow-up form should be completed for each follow-up visit, and all adverse reactions should be recorded on the follow-up form

12.3 The main adverse reactions include: swelling and pain of the breast on the affected side, acute radiation dermatitis, radiation pneumonia, breast beauty effect, radiation heart injury, radiation pulmonary fibrosis, lymphatic edema, brachial plexus neuralgia

12.4 Adverse reactions were graded using the CTCAE 3.0 standard, and lymphedema was assessed using the arm, shoulder and hand disability questionnaire (QuickDASH-9, clinical lymphedema was defined as at least one reported relative percentage difference of 10% or more compared to the baseline, healthy upper limb) and the arm symptom subscale of cancer treatment function assessment-breast +4 (FACT-B+4)

12.5 Physical examination

12.6 Breast beauty evaluation (including physical examination and breast photos)

13. Quality of life assessment

13.1 Chinese version of EORTC QLQ-C30 scale and QLQ-BR23 scale

13.2 Assessments are performed before, after and at 1, 3, 6, 12,18 and 24 months post-radiation therapy

Basic Requirements :

1) The CRF should be completed for each follow-up visit, and all adverse reactions should be recorded on the follow-up form.

- 2) The evaluation criteria for acute and late radiotherapy adverse reactions were based on CTCAE 3.0.
- 3) Upper limb edema was compared with the baseline and the measurement of the circumference of the healthy upper arm. If the increase was more than 10%, edema was considered to exist.
- 4) For the evaluation of skin injury and upper limb dysfunction, photos and videos are preferred.
- 5) Adverse reactions occurring 3 months after the start of radiotherapy are considered as late adverse reactions.

reference documentation :

1. 1. Benitez Fuentes, J. D. et al. Global Stage Distribution of Breast Cancer at Diagnosis: A Systematic Review and Meta-Analysis. *JAMA Oncol.* 10, 71 (2024).
2. 2. Wang, Q. et al. Breast cancer stage at diagnosis and area-based socioeconomic status: a multicenter 10-year retrospective clinical epidemiological study in China. *BMC Cancer* 12, 122 (2012).
3. 3. Bahadoer, R. R. et al. Short-course radiotherapy followed by chemotherapy before total mesorectal excision (TME) versus preoperative chemoradiotherapy, TME, and optional adjuvant chemotherapy in locally advanced rectal cancer (RAPIDO): A randomised, open-label, phase 3 trial. *Lancet Oncol.* 22, 29 – 42 (2021).
4. 4. Kong, X. et al. Revolutionizing the battle against locally advanced breast cancer: A comprehensive insight into neoadjuvant radiotherapy.
5. 5. Litton, J. K. et al. Standardized definitions for efficacy end points in neoadjuvant breast cancer clinical trials: NeoSTEEP. *J. Clin. Oncol.* 41, 4433 – 4442 (2023).
6. 6. Costa, S. D. et al. Neoadjuvant Chemotherapy Shows Similar Response in Patients With Inflammatory or Locally Advanced Breast Cancer When Compared With Operable Breast Cancer: A Secondary Analysis of the GeparTrio Trial Data. *J. Clin. Oncol.* 28, 83 – 91 (2010).
7. 7. Cortazar, P. et al. Pathological complete response and long-term clinical benefit in breast cancer: The CTNeoBC pooled analysis. *The Lancet* 384, 164 – 172 (2014).
8. 8. Rastogi, P. et al. Preoperative chemotherapy: Updates of national surgical adjuvant breast and bowel project protocols B-18 and B-27. *J. Clin. Oncol.* 26, 778 – 785 (2008).

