Research overview

Title: Prospective phase II clinical study of neoadjuvant chemotherapy combined with preoperative radiotherapy in locally advanced breast cancer

Applicant: Shenzhen Hospital, Cancer Hospital, Chinese Academy of Medical Sciences

Type of study: A clinical trial initiated by the investigator

Study subjects: Patients with locally advanced luminal (HER2-) and triple-negative breast cancer

Objective: To prospectively evaluate the efficacy and safety of neoadjuvant chemotherapy combined with preoperative large fraction radiotherapy followed by surgery in breast cancer

Study design: A prospective phase II clinical study

Number of patients planned to be enrolled: 50

Clinical trial unit: Shenzhen Hospital, Cancer Hospital, Chinese Academy of Medical Sciences

Radiotherapy: whole breast irradiation of the affected side \pm chest wall + regional lymph node drainage area irradiation: whole breast \pm chest wall + supraclavicular and internal mammary regional lymph node drainage area 40.05Gy/152.67Gy/ day per session, axillary regional lymph node drainage area 37.5Gy/15f,2.5Gy/ per session

Primary endpoint: pCR rate (pathological complete response rate)

Secondary safety indicator 1: incidence of acute adverse reactions during chemoradiotherapy (including acute skin injury, breast swelling and pain, local infection, radiation mucositis, radiation pneumonia, upper limb lymphedema rate, blood biochemical reaction and systemic reaction, etc.)

Secondary safety indicators 2: Postoperative complication incidence (delayed incision healing rate, secondary surgery rate), late adverse reaction incidence (including late skin injury, breast swelling and pain, cosmetic effect, radiation cardiomyopathy,

pulmonary fibrosis, radiation brachial plexus injury, upper limb lymphedema), quality of life (EORTC QLQ30, BR-23 questionnaire)

Secondary efficacy indicators: local recurrence rate, regional recurrence rate, pathological response rate (according to Miller-Payne classification), npCR (near npCR) rate, RCB (residual tumor burden) rate, event-free survival rate, distant metastasis rate, tumor-free survival rate, and overall survival rate

Biological research: Collect fresh tumor tissue and peripheral blood before treatment and surgery as test samples to evaluate biological markers such as tumor gene expression, circulating tumor cells, inflammatory factors, ctDNA, etc.

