3.1 Primary study endpoint: pCR rate (pathological complete response rate)

3.2 Secondary study endpoints:

3.2.1 Early adverse reactions: acute skin injury, breast swelling and pain, local infection, radiation mucositis, radiation pneumonia, upper limb lymphedema rate, blood biochemical reaction and systemic reaction

3.2.2 Other adverse events:

Postoperative complication rate (delayed incision healing rate, secondary surgery rate), late adverse reaction rate (including late skin injury, breast swelling and pain, cosmetic effect, radiation cardiomyopathy, pulmonary fibrosis, radiation brachial plexus injury, upper limb lymphedema), quality of life (EORTC QLQ30, BR-23 questionnaire)

3.2.3 Efficacy indicators: local recurrence rate, regional recurrence rate, pathological response rate (according to Miller-Payne classification), npCR (near npCR) rate, RCB (residual tumor burden) rate, event-free survival, distant metastasis rate, tumor-free

survival rate, and overall survival rate

3.2.4 Transformation research indicators:

Tissue samples: including pre-adjuvant therapy and surgical specimens. Some are used for organoid construction; others are used for single-cell sequencing; paraffin tissue samples: some tissue blocks are fixed in centrifuge tubes containing formalin, which can be used for spatial transcriptome sequencing.

Peripheral blood samples: The plasma part can detect immune factors and ctDNA, and PBMC (peripheral blood mononuclear cells) can be enriched by flow or mass spectrometry, as well as T and NK. CTDNA is planned to collect 5-10 patients.

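### One 3-month clock from the start of preoperative radiotherapy classes acute skin reactions to the postoperative boost as late skin injury

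*Protocol*

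**What the plan says.** The rule that separates early from late reactions is in Section 13, Basic Requirements, item 5: "Adverse reactions occurring 3 months after the start of radiotherapy are considered as late adverse reactions". It names one starting point and gives no second one for radiotherapy delivered later.

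Section 6.3 sets the preoperative course: "both are 5 times per week and completed in 3 weeks". Section 7 places two chemotherapy cycles before radiotherapy and four after it, and the overview's roadmap puts surgery after those four. Section 7 also lets surgery be considered if shrinkage is still under 50% after four cycles.

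Section 6.4 then adds radiotherapy after the operation. For the breast: "If the primary lesion after surgery does not reach pCR, the tumor bed is increased to 13.35Gy/2.67Gy/5F". For an axilla without R0 resection: "Residual lymph nodes should be routinely divided with 26Gy/13F after surgery".

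Early and late reactions are separate secondary endpoints in Section 3.2. Section 3.2.1 lists "Early adverse reactions: acute skin injury, breast swelling and pain, local infection, radiation mucositis, radiation pneumonia, upper limb lymphedema rate" and further items. Section 3.2.2 lists "late adverse reaction rate (including late skin injury, breast swelling and pain, cosmetic effect" and others. Skin injury is in both lists, distinguished only as acute or late. The overview words the acute endpoint as "Secondary safety indicator 1: incidence of acute adverse reactions during chemoradiotherapy".

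**The concern.** An early/late cut counted from the start of radiotherapy works when there is one course. Here there can be two, separated by months of chemotherapy and an operation. Dermatitis during the second course is an acute reaction to that course, but item 5 classes it by the time since the first fraction of the first course.

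The aim in Section 2.2 is to establish the safety and feasibility of preoperative radiotherapy as a basis for phase III. If short-lived boost dermatitis enters the late rate, that rate no longer describes lasting harm from the preoperative course. The tumour-bed boost goes only to patients whose primary lesion is not in pCR, so the added events all fall in that group and late skin injury would look linked to poor response. A single arm has no control group in which the shift would show.

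**Working it through.** The cut is a definition, so there is no stated figure to reproduce. The check is a timeline in weeks from the first preoperative fraction.

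**From the protocol**
- Cut: 3 months (Section 13, item 5) = 3 × 365.25 / 12 / 7 = 13.04 weeks.
- Preoperative course: 3 weeks (Section 6.3).
- Cycles between radiotherapy and surgery: n = 4 on the planned route (Section 7). If the four-cycle option means four in total, n = 2.
- Boost: after surgery (Section 6.4).

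**Assumed, because the protocol does not say**
- Cycle length c: 2 or 3 weeks.
- Gap g from the end of radiotherapy to the next cycle: 0 to 2 weeks.
- Interval r from the last chemotherapy dose, taken as the start of the last cycle, to surgery: 2 to 4 weeks.
- Healing h from surgery to the boost: 3 to 8 weeks.

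**Formulas**

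Surgery S = 3 + g + (n − 1)c + r. Boost start B = S + h.

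| Route | c | S earliest | S latest | B range | Against 13.04 |
|---|---|---|---|---|---|
| Six cycles, n = 4 | 3 | 3+0+9+2 = 14 | 3+2+9+4 = 18 | 17 to 26 | all after |
| Six cycles, n = 4 | 2 | 3+0+6+2 = 11 | 3+2+6+4 = 15 | 14 to 23 | all after |
| Four cycles in total, n = 2 | 3 | 3+0+3+2 = 8 | 3+2+3+4 = 12 | 11 to 20 | both sides |
| Four cycles in total, n = 2 | 2 | 3+0+2+2 = 7 | 3+2+2+4 = 11 | 10 to 19 | both sides |

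**Sensitivity.** On the fastest six-cycle timeline the boost falls after the cut once healing exceeds 13.04 − 11 = 2.04 weeks. With exactly 2 weeks it would start at week 13, at the cut. Slower timelines only move it later.

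**Side check.** Section 1 cites intervals of 6 to 12 weeks between preoperative radiotherapy and surgery in the literature. Counted from the end of radiotherapy, that is 9 to 15 weeks from its start. This is background and not a trial rule; its low end does not accommodate four cycles even at 14 days, which give 11 weeks under the assumptions above.

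**Effect per patient.** With 50 patients as the denominator, each patient whose only late skin event is an acute boost reaction adds 1/50 = 2 percentage points to the late skin injury rate.

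**The case against.** The strongest reply is that the effect is narrow. Only labels on secondary safety endpoints change, and pCR is untouched. Reactions are recorded at each follow-up visit, so they could be reclassified if onset dates are kept. The follow-up table in the Appendix is not shown, and analysis windows may be set in a statistical analysis plan. The limits on scope stand. But item 5 is not a gap left for a later document: it is a stated rule that gives the wrong class.

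It can also be said that the timing is assumed. That is true, and surgery itself may fall before or after the cut. The conclusion about the boost on the six-cycle route nevertheless holds for both cycle lengths.

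A reader might infer more than the documents support:
- **A definite number of patients.** Applying the background rates of 15% and 35% gives 50 × 0.85 = 42.5 and 50 × 0.65 = 32.5 patients without pCR. But the 15% in Section 1 is a complete response rate listed beside objective and partial response, and is not called pCR. The boost depends on the primary lesion alone, whereas Section 9.5 defines pCR on breast and nodes together. Some patients will have mastectomy, and some will take the early-surgery route.
- **An acute rate that looks too good.** The overview limits the acute endpoint to the chemoradiotherapy period, so leaving postoperative boost reactions out of it is defensible. A patient with dermatitis from the preoperative course is already counted there.
- **Misfiled surgical swelling and late-cycle blood counts.** Item 5 stands among rules for radiotherapy reactions. These are not clearly radiotherapy reactions, surgical complications have their own endpoint, and the late list has no blood item.

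**Conclusion.** The point holds for the postoperative boost. On the six-cycle route, with 14- or 21-day cycles and 3 to 8 weeks of healing, the boost starts about 14 to 26 weeks after the start of radiotherapy, so item 5 makes its acute skin reactions late skin injury. If surgery follows four cycles in total, the boost starts at about 10 to 20 weeks, and the same reaction is early or late depending on route and timing. Enrolment selects tumours that shrank by less than 50% after two cycles, so the shorter route may well be used.

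The main consequence is a late skin injury rate that is too high in patients without pCR of the primary. Its size cannot be fixed, because the documents give neither the number boosted nor the frequency of boost reactions. The case for an understated acute rate is weak, and the primary endpoint is not affected.

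**What to change.** Keep item 5 for reactions to the preoperative course, counted from its first fraction, and add one sentence: a reaction at the boosted site with onset between the first postoperative boost fraction and 3 months after it is an acute reaction to the boost, is reported separately from the preoperative acute rate, and counts as late only if it persists beyond that window.

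The clock for the preoperative course should stay where it is. Moving the late window to 3 months after surgery or boost for everyone would make the early/late boundary depend on response, because the tumour-bed boost does.

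There is one small downside. A new reaction at the boosted site in that window may be a true late effect of the preoperative course. The report should therefore also show late skin injury with these events included.

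The cost is one sentence, matching words in the endpoint lists, and three items on the case report form: date of the first boost fraction, onset date and site of the reaction. Treatment and sample size do not change and no new visit is proposed, though the Appendix table should be checked for an assessment during or soon after the boost.
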